### **5.3 DATA MANAGEMENT**

All data will be entered by trained research assistants using REDCap software. Double data entry will be required for information not directly entered by the participants. Double data entry will also be entered by trained research assistants using REDCap software. All data analysis will be conducted by statistician, [name].

### **6** RISKS AND BENEFITS

There are some risks associated with the proposed research. First, collection of the clinical information may be associated with anxiety or embarrassment due to revealing personal information. Second, there is the risk that confidential personal information could be disclosed to others outside of the research staff. Third, there is risk in participating in the 6-minute walk test, Chair-Rise task, and 2-minute Step Test as a measure of cardiorespiratory fitness (CRF). Finally, there is risk associated with participating in the walking groups, such as ankle, leg, and back injuries, and cardiovascular distress.

### **6.1 Monitoring Risks**

To address subject anxiety or embarrassment due to revealing person information, we have trained research staff who are experienced in working with individuals with schizophrenia spectrum disorders. They have been trained to put subjects at ease, let them take their time, and to conduct interviews in private rooms.

To address the issue of accidental disclosure of personal information to others outside of the research staff, we will obtain a NIH Certificate of Confidentiality for the study. In addition, identifying research subjects by study number on all research documents minimizes the risk of breach of confidentiality. Study documents that must contain personal information, including the informed consent document, and the document that links study ID number to personal identifying information (necessary due to the longitudinal nature of the open trial and RCT) are kept in locked filing cabinets in locked rooms. Research data will be kept on password-protected drives, and our computer systems are HIPAA compliant. All study staff participate in annual human subject training that includes education about responsibilities to minimize risk that confidentiality may be breached.

To address the potential health risk associated with participation in the walking groups as well as the 6-minute-walk-test, chair-rise task, and 2-minute step test, all subjects will obtain medical clearance from their general practitioner, or have a medical history and physical examination performed by [name] as part of the Screening procedures. [name] and/or a trained research assistant will also administer the PAR-Q, a widely used questionnaire to assess cardiovascular risk factors in advance of exercise initiation. For any subject who answers "yes" to one or more items on the PAR-Q, [name] and/or a trained research assistant will contact their PCP to discuss appropriateness for the subject to participate and help facilitate further evaluation as needed. In addition, the research staff will be trained by one of the PIs, [name], an exercise physiologist, on the 6-minute-walk-test, chair-rise task, and 2-minute step test procedures. Further, if an individual shows any distress during this assessment, she or he will be instructed to stop the assessment and the research staff will contact [name] and [name].

To address the issue of physical injury or cardiovascular distress during the walking groups, the study clinicians will be trained by [name] on potential cardiovascular warning signs, and appropriate responses to any reported symptoms. Further, a safety plan for the walking groups will be developed prior to the initiation of the study with Drs. [name] and [name], as well as the study clinicians. The walking groups will be conducted on level terrain, to minimize any potential leg, ankle or back injuries. Finally, it should be emphasized that this project is testing the impact of moderate-intensity walking, a less physically demanding and inherently safer activity when compared to other more rigorous activities that could pose greater cardiovascular and joint-related risks.

Should any subject experience any problems during the study, our research team has trained staff that will be able to provide immediate care on-site. Subjects will be referred for additional care to the appropriate

providers on campus, such as Campus Health Services or the UNC Hospitals Emergency Department, if necessary.

### 6.2 NON-SIGNIFICANT RISK DOCUMENTATION

Pregnant women will be excluded because pregnancy alters autonomic and immune responsiveness, increase weight gain, and can influence heart rate.

### 6.3 POTENTIAL BENEFITS OF THE RESEARCH TO SUBJECTS AND OTHERS

The subjects who participate in the walking groups (in the open trial and RCT) may have a significant benefit on their cardiorespiratory fitness, which could have a subsequent impact on their overall physical and mental health. This study will provide currently unavailable information about the potential feasibility and effectiveness of a scalable and accessible exercise intervention for individuals with schizophrenia spectrum disorders. The risks of the study are minimal and reasonable in light of the knowledge gained.

### 6.4 CONFIDENTIALITY OF DATA

Risks regarding confidentiality will be minimized by using code numbers instead of names on study data. The code and the data will be stored in separate locked files at Davie or Howell Hall on UNC's campus. Similar subject records are scrutinized regularly and our procedure will add an extra level of protection because the research case numbers will be different from subject numbers (random numbers not associated with date of birth) and the code will be unavailable to anyone outside of the research team. Audio recordings of weekly group sessions will be saved on our secure lab server and on OneDrive so that offsite investigators may review and provide feedback to the clinicians conducting the sessions.

Identifiable data will only be shared with the clinicians of subjects in the study with the permission of the subjects (obtained during informed consent). Clinicians will be contacted if issues arise related to safety during the trial. As part of the informed consent process, all subjects will provide the name and contact info of a clinician that we may contact if we become concerned about their safety (e.g., physical and/or mental health) during the course of the trial. We will not be sharing any confidential information with anybody outside of these clinicians.

Identifiable data will be maintained for 5 years following study completion. At that point, hard copies of identifiable data including consent forms and contact information will be shredded. Electronic data will be de-identified upon entry, with the exception of the subjects' birth dates for the purposes of calculating their exact age.

### 7 DATA SAFETY AND MONITORING PLAN

### 7.1 ADVERSE EVENTS

[name] (Co-I) will function as the Project Medical Officer and will be available on pager and cell phone to all co-investigators to discuss any safety issue that emerges over the course of the study. All adverse events (AEs) occurring during the course of the study will be documented and reported to [name]. All Serious Adverse Events (SAEs) will also be reported to the IRB and NIMH. The occurrence of AEs will be assessed during the study and the investigators will follow all AEs to the point of satisfactory resolution. An independent physician will serve as Medical Monitor ([name], from the Department of Psychiatry). AEs will be tracked over the course of the study and will be reported at the midpoint and endpoint of each walking group cohort to the DSC. All SAEs will be reported to the DSC within 24 hours of learning of the event.

### 7.2 SERIOUS ADVERSE EVENTS

AEs will be assessed to determine if they meet criteria for a SAE. SAEs, as defined by the FDA, will be systematically evaluated at each clinic visit. Any SAE will be reported to the IRB and NIMH. The initial SAE report will be followed by submission of a completed SAE report to each institution. In the event that a subject either withdraws from the study or the investigator decides to discontinue a subject due to SAE, the subject will have appropriate follow-up and/or stabilization. Follow-up will continue until the problem requiring hospitalization has resolved or stabilized with no further change expected, is clearly unrelated to study procedures, or results in death. Outcome of SAEs will be periodically reported to NIMH. A summary of the SAEs that occurred during the previous year will be included in the annual progress report to NIMH.

The trial period is defined from the time that the informed consent document is signed until 30 days after the last study visit. All serious AE's occurring during the trial period (including death due to any cause) or within 30 days after the last study visit will be communicated within 1 day of the investigator becoming aware of the event to designated personnel, using the telephone or fax numbers provided in the Study Reference Manual. Any fatal or life-threatening AE's will be reported immediately, but no longer than 1 day from the time the investigator becomes aware of the event. A causality assessment will be provided for all SAEs. Critical follow-up information on SAEs will be provided as soon as it is available, but no longer than 1 day from the time the investigator became aware of the information. Other essential, but not critical, information may be reported within the following 5 days. An SAE, as defined by the FDA for use in clinical trials https://www.fda.gov/safety/medwatch/howtoreport/ucm053087.htm), is an adverse event that satisfies any of the following criteria:

- Results in death.
- Is immediately life-threatening, including potentially life threatening suicidal behavior or suicidal behavior that results in hospitalization.
- Requires inpatient hospitalization or prolongation of existing hospitalization.
- Results in persistent or significant disability or incapacity.
- Is a congenital abnormality or birth defect.
- Is an important medical event that may jeopardize the subject or may require medical intervention to prevent one of the outcomes listed above. Examples would include allergic bronchospasm that requires treatment in an emergency department, or a seizure that does not result in hospitalization.

The causality of SAEs (i.e., their degree of relatedness to study treatment) will be assessed by the investigators.

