Rationale for clinic-based/home-based rather than a gym-based exercise intervention. We propose to provide PACE-life through a mental health clinic as individuals with SSDs usually have frequent contact with their providers. Furthermore, interventions that don't require additional equipment or supervision by an exercise trainer have greater potential for integration into healthcare services for individuals with SSDs. Our rationale for a clinic-based versus a gym-based exercise program is also based upon recommendations for integrated medical care (104) as well as integrated physical activity within mental health services for this population (105). In addition to clinic-based sessions, we will include home-based sessions, which can be completed at any location and time of the subjects' choosing to improve self-management and facilitate longterm exercise adoption. The term, "home-based," means only that individuals will be engaging in this component independently and do not need to attend a select location or require additional equipment. We will work with subjects to identify convenient walking routes using websites and apps (e.g. map my walk). Therefore, our intervention will include both clinic-based sessions and instructions for home-based sessions to prioritize feasibility and sustainability. Moreover, given the disruption of the COVID-19 pandemic, we've redesigned our study to have feasibility in a virtual format. Subjects can participate in the study from their homes, as we provide them with technology (e.g., tablets and data plans) necessary for participating in virtual exercise sessions. Exercise sessions include dynamic, stationary exercises that model walking movements, to best match movements performed in outdoor walking sessions. These obstacles have provided the research team with an opportunity to learn about the sustainability and scalability of home-based virtual interventions, in addition to clinic-based interventions.

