### 4 STUDY DESIGN

During this phase of the trial, 56 subjects will be assigned to the fitbit only group (control) or the PACE-Life walking group (intervention). The exercise intervention, PACE-Life, will last for 16 weeks and includes both group walks and independent walks (done at a location of the subject's choosing). Subjects will be asked to complete a total of 5 in-person, or virtual assessments at screening, baseline, mid-point, post-test, and 1-month follow-up.

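### Scheduled systematic SAE evaluation is tied to an undefined clinic visit although participation may be virtual, and AE collection between visits is unspecified while scheduled contact differs widely by arm

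*Combined protocol and SAP*

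**What the plan says.** Section 7.2 sets the timing of systematic SAE evaluation: "SAEs, as defined by the FDA, will be systematically evaluated at each clinic visit". It does not say what counts as a clinic visit. The same section has AEs screened against the SAE criteria.

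Section 7.1 is broader but less specific. "The occurrence of AEs will be assessed during the study and the investigators will follow all AEs to the point of satisfactory resolution". It also requires all AEs during the study to be documented and, on reporting to the DSC, states that "AEs will be tracked over the course of the study and will be reported at the midpoint and endpoint of each walking group cohort". SAEs must reach the DSC within 24 hours of the team learning of them. No question set, interval or responsible collector is given.

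On where participation takes place, Section 4 states: "Subjects will be asked to complete a total of 5 in-person, or virtual assessments at screening, baseline, mid-point, post-test, and 1-month follow-up". Section 2.1 adds that "Subjects can participate in the study from their homes". Section 4.1 puts virtual walking sessions on video calls that can be joined from home. Section 4.2.2 allows blood pressure and resting heart rate to be taken at home, on campus or at the Wake STEP clinic for those with virtual visits. Section 4.1, however, also places all assessments in a conference room at the clinic.

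On care, Section 6.1 says that "our research team has trained staff that will be able to provide immediate care on-site".

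**The concern.** The safety text appears to have kept its in-person wording after the virtual format was added. If staff follow Section 7.2 as written, a participant assessed entirely by video is not clearly covered by the scheduled SAE evaluation. Section 7.1 does not settle this, because it says that AEs will be assessed without saying how.

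The arms also differ in how often anyone from the study meets the participant. The PACE-Life arm has group sessions twice a week, and Section 6.1 has study clinicians trained on cardiovascular warning signs and on responding to reported symptoms in those groups. No matching contact is described for the Fitbit-only arm. Without a common method of asking, events between visits come to light mainly when a participant happens to mention them, and one arm has far more occasions to do so.

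Two things are at stake: capture of events in people exercising at home, where Section 6 names injury and cardiovascular distress as risks, and the meaning of any event counts later set out by arm.

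**Working it through.** The plan states no SAE rate, detection rate or safety power, so there is no figure to reproduce. The check compares the sections, counts scheduled contacts, and then gives an illustration on assumed inputs.

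**1. Is there a scheduled SAE evaluation that clearly covers a virtual visit?**

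- Section 7.2: systematic evaluation at clinic visits; term undefined.
- Section 4: all five assessments may be virtual.
- Section 4.2.2: the measures listed for baseline, mid-point, post-test and follow-up contain no AE or SAE item.
- Section 7.4: an adverse events form exists, but is mentioned only for pregnancy.
- Section 7.1: AEs are assessed and tracked throughout, with no method.

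No section says that a virtual assessment counts as a clinic visit, and none says that it does not.

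**2. Scheduled post-baseline contacts by arm**

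Inputs: 16 weeks (Section 4); 2 group sessions a week (Section 4.1); 3 post-baseline assessments, namely mid-point, post-test and 1-month follow-up (Section 4).

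- PACE-Life: 16 × 2 + 3 = 35
- Control: 3
- Ratio: 35 / 3 = 11.7

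The in-person table in Section 4.1 runs to week 24, which conflicts with the 16 weeks in Section 4. On that table the count is 24 × 2 + 3 = 51 against 3, a ratio of 17. Goal-setting groups are not counted separately, because Section 4.1.1 does not give their number.

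**3. Illustration of unequal detection (assumed inputs)**

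Assume the same true event risk in both arms, detection of 0.95 in PACE-Life, and detection of 0.60 to 0.80 in control. None of these values is in the plan.

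- Apparent risk ratio = detection in PACE-Life / detection in control
- 0.95 / 0.80 = 1.19
- 0.95 / 0.60 = 1.58

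With 28 per arm (Section 5.2) and an assumed true risk of 10%, the expected recorded events are:

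- PACE-Life: 28 × 0.10 × 0.95 = 2.66
- Control: 28 × 0.10 × 0.80 = 2.24, down to 28 × 0.10 × 0.60 = 1.68

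Equal detection gives a ratio of 1.00 whatever its level, which is what a common question set at common visits aims for.

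**4. What a by-arm comparison could show anyway**

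For two proportions with 28 per arm and two-sided alpha 0.05 (normal approximation), about 80% power needs differences as large as 5% against 35% (power 0.82) or 10% against 43% (power 0.82). Any by-arm safety table would be descriptive however events are collected.

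**The case against.** The strongest reply is that Section 7.2 simply retains pre-pandemic wording for visits that are now partly virtual. Section 4 gives one assessment schedule to all participants, Section 4.2.2 calls the remote ones study visits, and the natural intent is that SAEs are asked about at each. Section 7.1 adds assessment, documentation and tracking of AEs not tied to any clinic. The walking-group safety plan and the Study Reference Manual, neither of which is in the document, may hold the missing detail.

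Much of this stands, and it rules out several stronger readings that a reader might infer:

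- *That SAEs are picked up only at clinic visits.* Section 7.2 does not say so, and Section 7.1 provides for AE assessment throughout. What is missing outside clinic visits is a stated method.
- *That a remote participant would receive no SAE evaluation.* This follows only from the most literal reading of an undefined term.
- *That the arms cannot be compared on safety.* The assessment schedule is common to both, so events elicited there in the same way would be comparable. No between-arm safety test is planned.
- *That the DSC receives event counts broken down by walking-group cohort.* Section 7.1 says when AEs are reported, not how they are tabulated.

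It is also fair that deaths and hospital admissions are likely to be recalled at the next assessment, so unequal contact should matter less for them than for minor events. That is a judgement; the document gives no data on it. The absence of further contact with controls is likewise inferred from silence.

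The reply does not remove the gap. The intended reading of Section 7.2 should not have to be guessed, and neither Section 7.1 nor the measures listed in Section 4.2.2 say how events are to be elicited.

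**Conclusion.** The point holds in a limited form. The one scheduled systematic SAE evaluation is attached to a term that does not clearly include virtual assessments, and collection between visits has no stated method. Events in remote participants may therefore be under-recorded. Events between visits, mainly non-serious AEs, may be detected more often in the PACE-Life arm.

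The firm figure is the contact imbalance: 35 against 3 scheduled post-baseline contacts over 16 weeks, taking the schedule as written and assuming that the silence about further control-arm contact means there is none. The apparent risk ratios of 1.19 to 1.58 rest wholly on assumed detection rates; they show the direction and a plausible scale, not an estimate. The planned efficacy analyses are unaffected. This is worth correcting because it concerns participant safety and costs little, but it does not invalidate the design.

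**What to change.** 1. In Section 7.2, replace the reference to clinic visits with each scheduled assessment, whether in person or virtual.
2. Add the same short set of AE and SAE questions, for both arms, to the measures in Section 4.2.2, and name it in Section 7.1 as the method of collection.
3. Record for each event whether it was elicited at a common assessment or volunteered at a group session.
4. Base any descriptive by-arm table on the elicited events, and list the volunteered ones separately.

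The cost is a short checklist at visits already scheduled, with no added visits.

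Separately, the on-site care statement in Section 6.1, and the statement in Section 4.1 that all assessments take place at the clinic, must be reconciled with home-based virtual participation. The 16-week duration in Section 4 and the 24-week in-person table in Section 4.1 must also be reconciled. How these are resolved is for the investigators.

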### 7.3 DEATH

All deaths occurring within the trial period or within 30 days after the last day that the study intervention is administered will be reported within 1 day of the investigator becoming aware of the event. If an autopsy has been performed, results of the autopsy will be obtained and forwarded along with any available toxicology reports.

### 7.4 PREGNANCY

Pregnancy is an exclusion criterion and women who can become pregnant should use adequate methods of birth control as outlined in the inclusion criteria. Should a pregnancy occur it must be reported in accordance with the procedures described below. Pregnancy in itself is not regarded as an AE unless there is a suspicion that an intervention may have interfered with the effectiveness of a contraceptive medication. However, the outcome of all pregnancies (spontaneous miscarriage, elective termination, normal birth or congenital abnormality) must be followed up and documented even if the subject was discontinued from the study. The Adverse Events/Side Affects form will be used for this purpose. All reports of congenital abnormalities/birth defects are SAE's. Spontaneous miscarriages should also be reported and handled as SAE's. All other outcomes of pregnancy must be reported on the Adverse Events/Side Effects form.

### 8 RECRUITMENT STRATEGY

Subjects will be recruited from various clinics in Durham, Carrboro, Chapel Hill, and Raleigh, North Carolina. Clinics and sites include the UNC Schizophrenia Treatment and Evaluation Program (STEP) clinics in Raleigh and Carrboro, the Outreach and Support Intervention Services (OASIS) program in Chapel Hill, Carolina Behavioral Care, Club Nova, and Threshold.. STEP, in particular, provides services to approximately 435 clients annually; 76% at STEP meet criteria for schizophrenia spectrum disorders (SSD). Clients will be approached about the study in a manner similar to what would happen in the real world outside of a research study. Specifically, psychiatrists, clinicians, and nurses will provide information to clients during appointments, groups, and in the clinic waiting area of a potential new exercise group. If the client is interested, then the research assistant will be notified to get in contact with the interested client. IRB approved flyers will also be posted at STEP.

We will supplement recruitment at STEP Wake, as needed, with assistance from the North Carolina Psychiatric Research Center (NCPRC) and STEP-Chapel Hill. [name] (Co-I) is the research director of the NCPRC. The NCPRC is co-located with the STEP clinic in Raleigh and has dedicated staff and space dedicated to outpatient research. The NCPRC is an outpatient research facility that is integrated into the UNC STEP Clinic of Wake County. The mission of the NCPRC is to study the pathophysiology of and advance treatments for schizophrenia and related disorders. Research conducted at the NCPRC is currently funded by the NIMH, NIDDK, foundations that support mental health research, and selective collaborations with the pharmaceutical industry. The NCPRC fosters active collaborative research both within and across departments at UNC-Chapel Hill and with other academic institutions. It also serves as a core facility where other investigators at UNC-Chapel Hill can conduct mental health-related research. STEP-Chapel Hill has 944 active clients. Over 75% have a psychotic disorder and approximately 56% are female. Finally, we will recruit individuals who have agreed to be contacted about future studies while they were subjects in past research studies conducted by [name] (~300 individuals with SSDs).

